# 8.3 Statistical analysis of other efficacy variable

The other efficacy variables are defined as:

- Percent change from baseline in BMD at the lumbar spine, total hip, and femoral neck at Month 3 as assessed by DXA DBPC Period
- Percent change from baseline in BMD at the lumbar spine, total hip, and femoral neck at the end of OL Treatment Period (Month 12) as assessed by DXA in subjects who are initially randomized to placebo in the DBPC Period and transition to romosozumab treatment for 6 months – OL Treatment Period

The derivation rules specified in Section 8.1.1 and Section 8.2.2 will be applied for the calculation of the other efficacy variables as well.

The ANCOVA method described in Section Error! Reference source not found. for the primary efficacy variable will be performed. For Month 12 analysis, Only descriptive statistics will be summarized.

# 9 PHARMACOKINETICS AND PHARMACODYNAMICS

Missing PK or PD values (either Baseline or postbaseline values) will not be imputed. Measurement values that are below the lower limit of quantification (BLQ) will be considered equal to the LLOQ/2 for all analyses. If more than 1/3 of the samples are BLQ at a particular visit no summary statistics will be calculated and only minimum and maximum values will be reported.

### 9.1 Pharmacokinetics

Pharmacokinetic variables will be analyzed for all subjects in the PK-PPS at both Month 6 and final analysis. The serum trough concentrations of romosozumab will be summarized based on the PK-PPS using descriptive statistics (n, geometric mean, 95% confidence interval for geometric mean, geometric CV%, mean, standard deviation, median, minimum value, maximum value) for the below analyses:

- Month 1-6 of romosozumab/romosozumab treatment group at 6-month analysis
- Month 1-12 of romosozumab/romosozumab treatment group at final analysis
- Month 1-6 of romosozumab/romosozumab group pooled with month 6-12 of placeborromosozumab treatment group at final analysis

Geometric mean (geometric coefficient of variation) and GeoMean (±95% CI) romosozumab serum concentration time profiles will be displayed graphically on a linear scale and semilogarithmic scale.

Spaghetti plots of concentration-time profiles will be displayed graphically on a linear scale and semi-logarithmic scale.

A population PK analyses will be conducted. Details of the analysis will be described in a separated data analysis plan and results will be reported separately.

### 9.2 Pharmacodynamics

Pharmacodynamic variables will be analyzed for all subjects in the PD-PPS at both Month 6 and final analysis.

For the BTMs (P1NP and sCTX), descriptive statistics (n, geometric mean, 95% confidence intervals, geometric CV%, mean, standard deviation, median, interquartile range, minimum value, maximum value) will be presented by treatment group. The following list of endpoints will be analysed:

- observed values, change from Baseline and percent change from Baseline at all planned visits
- maximum on-treatment observed values, change from Baseline and percent change from Baseline (P1NP only)
- minimum on-treatment observed values, change from Baseline and percent change from Baseline (sCTX only)

Pharmacodynamic-time plots in P1NP and sCTX with median+/-interquartile range will be generated for the actual value and percent change from Baseline for each PD parameter at each visit for both the romosozumab and placebo group and these plots will be displayed on a linear scale.

For all PD endpoints, the following analyses are performed at:

• romosozumab treatment group vs. placebo group for month 1-6 at Month 6 analysis

romosozumab/romosozumab treatment group for month 1-6 vs. placebo/romosozumab notilation treatment group for month 6-12 at final analysis

#### **SAFETY ANALYSES** 10

Safety will be presented by treatment groups for the SS.

#### 10.1 **Extent of exposure**

The number of doses received will be summarized categorically (eg., 1, 2, 3, ...) and with descriptive statistics. In addition, the cumulative duration of exposure will be summarized for subjects exposed for different duration categories (eg., at least one day,  $\geq 1$  months,  $\geq 2$  months,  $\dots$ ,  $\geq$ 12 months).

Duration of exposure to IMP will be calculated as:

Date of last administration of IMP – date of first IMP administration +

Additionally, adjusted duration of exposure is calculated as:

Date of last administration of IMP – date of first IMP administration + 30 days - cumulative gaps in exposure

Calculate cumulative gaps are the number of days from date of previous dose + 30 days to next dose date summed up over the entire period. If subjects had gap of <=30 days between successive doses then gap in exposure will be 0 days for this period.

#### Adverse events c 10.2

Treatment emergent AEs (TEAE) are defined as all AEs started or worsened in severity on or after the date of receiving first dose of IMP and before EOS date except lipid-type AEs starting on the date of first dose of IMP and not worsening (and not deemed IMP related by the investigator). Lipid-type AEs will be defined by the Dyslipidaemia SMQ (see Appendix 13.7). The different handling of lipid-type AEs starting on the date of first dose of IMP is to ensure that pre-existing lipid abnormalities are not reported as TEAEs (lipids are only measured at Day 1 before first IMP and not at Screening).

All subsequently described displays in Section 10.2 will be compiled for the DBPC Period and for the overall study period (treatment start through Month 15). For the displays on the DBPC Period, TEAEs with a start date before or on the End of DBPC period date will be included. For the overall period, TEAEs with a start date before or on the EOS date will be included.

Duration of AEs will not be calculated if there is missing stop date information. If the intensity of an AE is unknown, it is considered as severe. If the relationship to study drug is missing, it is considered as related. Note that if the seriousness of an adverse event is unknown, every attempt should be made to resolve this prior to a snapshot for an interim analysis or database lock; in the exceptional case that the seriousness of an adverse event is still missing then no imputation should be applied for this characteristic.

If a TEAE occurs on the date of switch from the DBPC period to the OL period, the event is attributed to the DBPC treatment. The only exception that TEAEs of injection site reactions (see Appendix 13.5), potentially related to hypersensitivity (Standardized MedDRA® Query [SMQ], narrow scope) will be in OL period.

The number and incidence of TEAEs will be summarized by treatment group, the MedDRA® SOC and PT with the SOC sorted alphabetically and within SOC the PT sorted by descending order of frequencies. The incidence of TEAEs will also be summarized by treatment group (including romosozumab total), intensity and relationship to IMP.

Adverse events will be presented as "number of participants (percentage of participants) [number of events]". In this style of output, "[number of events]" will include all cases of an AE including repeat occurrences in individual participants, while "number of participants" will count each participant only once.

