3.2.3 Safety objectives

The safety objectives will be presented for the OL Treatment Period (up to Month 12) and for the overall study period that includes the 3-month Follow-Up Period (for a total of 15 months) as follows:

- To characterize the safety and tolerability of romosozumab treatment in postmenopausal Chinese women with osteoporosis who are continuing with 6 months of romosozumab treatment after initially being randomized to 6 months of romosozumab treatment in the Double-Blind, Placebo-Controlled Period (for a total of 12 months of romosozumab treatment).
- To characterize the safety and tolerability of romosozumab treatment in postmenopausal Chinese women with osteoporosis who are initially randomized to placebo in the Double-Blind, Placebo-Controlled Period and transition to romosozumab treatment.

STUDY VARIABLES 4

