4.2.3.1 Primary safety variable

The primary safety variable is the overall incidence of TEAEs.

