# 2.4.3 Safety variables

The safety variables listed below will be assessed during the OL Treatment Period, including some selected safety variables that will be followed up to Month 15, in subjects who are initially randomized to 6 months of romosozumab treatment in the DBPC Period and continue with romosozumab for 6 months (for a total of 12 months of romosozumab treatment) and in subjects who are initially randomized to placebo in the DBPC Period and transition to romosozumab treatment for 6 months.

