# 10.2.2 Exposure adjusted incidence rate (EAIR) and exposure adjusted event rate (EAER)

Selected AE summaries will include the EAIR with associated 95% confidence interval and EAER where the EAIR and EAER are expressed per 100 study participant-years of exposure.

The EAIR is defined as the number of participants (n) with a specific AE adjusted for the exposure and will be scaled to 100 study participant-years:  $EAIR = 100 \times \frac{n}{\sum_{i=1}^{N} (T_{EXP(i)})}$ 

where n is the total number of participants with AE of interest, N= number of participants at risk of an AE, and  $T_{Exp(i)}$  is the total exposure time for each participant:

- For participantss with the specific AE of interest:time at risk in years to the first occurrence for the AE of interest at the level of coding evaluated
- For participantss without the AE: the total time at risk in years.

Exact Poisson 95% confidence intervals for incidence rates are calculated using the relationship between the Poisson and the Chi-square distribution (Ulm, 1990; Fay and Feuer, 1997):

$$LCL = \frac{x_{2n,\alpha/2}^2}{2}$$

$$UCL = \frac{x_{2(n+1),1-\alpha/2}^2}{2}$$

Confidential Page 39 of 89

UCB Statistical Analysis Plan 03 Mar 2023 OP0002

where n is the number of participants with a specific AE for the incidence rate of interest and is the basis for the number of the degrees of freedom for the chi-square quantile for the upper tail probability  $\chi 2$ .

The EAER will be the number of AEs including repeat occurrences in individual participants divided by the total time at risk scaled to 100 study participant-years and calculated using:

$$EAER = 100 \times \frac{N_{AE}}{\sum_{i=1}^{N} (T_{Risk(i)})}$$

where is the total number of AEs, n is the total number of participants and  $T_{Risk(i)}$  is the time at risk in years for each participant for each exposure period.

No confidence interval will be computed for EAER.

The following summaries will be provided by actual treatment group for the DBPC and the Overall Periods based on the SS. In addition, all summaries of TEAEs based on "100 participant-years" will include EAIR (with 95% confidence interval) and EAER.

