### 10.2.3 Standard AE summaries

- TEAEs overview during DBPC period
- TEAEs overview per 100 patient-years during overall period
- TEAEs by SOC and PT during DBPC period
- TEAEs per 100 patient-years by SOC and PT during overall period
- TEAEs by maximum intensity by SOC and PT during DBPC period
- TEAEs by maximum intensity by SOC and PT during overall period
- TEAEs by maximum relationship to IMP per the Investigator by SOC and PT during DBPC period
- TEAEs by maximum relationship to romosozumab per the Investigator by SOC and PT during overall period
- TEAEs leading to IMP discontinuation by SOC and PT during DBPC period
- TEAEs leading to romosozumab discontinuation by SOC and PT during overall period
- TEAEs leading to study discontinuation by SOC and PT during DBPC period
- TEAEs leading to study discontinuation by SOC and PT during overall period
- TEAEs leading to death by SOC and PT during DBPC period
- TEAEs leading to death by SOC and PT during overall period
- Serious TEAEs by SOC and PT during DBPC period
- Serious TEAEs per 100 patient-years by SOC and PT during overall period
- Serious TEAEs by maximum relationship to study medication per the Investigator by SOC and PT during DBPC period

Confidential

- Serious TEAEs by maximum relationship to study medication per the Investigator by SOC and PT during overall period
- Fatal TEAEs by maximum relationship to study medication per the Investigator by SOC and PT during DBPC period
- Non-serious TEAEs above reporting frequency threshold of 5% by SOC and PT during DBPC period

  Non-serious TEAEs above reporting frequency threshold of 5% by SOC and PT during DBPC period
- Non-serious TEAEs above reporting frequency threshold of 5% by SOC and PT during overall period

  TEAEs of interest by SOC and PT during DBPC period

  TEAE of special interest (PDILI) by SOC and PT during DBPC period

- TEAE of special interest (PDILI) by SOC and PT during DBPC period
- TEAEs of special interest (PDILI) by SOC and PT during overall period
- TEAEs of COVID-19 vaccine by SOC and PT during DBPC period

TEAEs of COVID-19 vaccine by SOC and PT during overall period There is no planned statistical testing in the safety analyses.

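### The SAP plans no adverse-event table for the open-label period, although TEAE incidence in that period is a stated primary safety variable, and its overall-period tables count events and time at risk from different starting doses

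*SAP*

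**What the plan says.** **What is required.** Protocol 3.2.3 says "The safety objectives will be presented for the OL Treatment Period (up to Month 12) and for the overall study period", for subjects who continue on romosozumab and for those who switch from placebo. SAP 2.2.3 repeats this. SAP 2.4.3 adds that "The safety variables listed below will be assessed during the OL Treatment Period", again in both sequences. Under the open-label heading, protocol 4.2.3.1 states "The primary safety variable is the overall incidence of TEAEs"; SAP 2.4.3.1 agrees.

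**What is planned.** SAP 10.2 says "All subsequently described displays in Section 10.2 will be compiled for the DBPC Period and for the overall study period", the latter running from the start of treatment to Month 15. The lead-in to the table list, at the end of SAP 10.2.2, says "The following summaries will be provided by actual treatment group for the DBPC and the Overall Periods based on the SS". Every title in SAP 10.2.3 that names a period names one of those two.

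**How overall-period events are counted.** SAP 10.2 says "Treatment emergent AEs (TEAE) are defined as all AEs started or worsened in severity on or after the date of receiving first dose of IMP"; the overall period takes every TEAE starting up to the end-of-study date. Protocol 7.1 counts placebo as IMP. SAP 10.2.1, however, starts overall-period time at risk at the first dose of romosozumab. Two overall titles in 10.2.3 refer to romosozumab where their double-blind counterparts refer to IMP: "TEAEs by maximum relationship to romosozumab per the Investigator by SOC and PT during overall period" and "TEAEs leading to romosozumab discontinuation by SOC and PT during overall period".

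**The concern.** A primary safety variable defined for the open-label period has no planned analysis. What would be missing is the share of about 100 switchers with a TEAE in their first 6 months on romosozumab, and the share of about 200 continuing subjects with one in their second 6 months.

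The second issue concerns the tables that are planned. In the placebo/romosozumab group, the overall-period event window opens about 6 months before the first romosozumab dose. A table whose title or denominator refers to romosozumab alone would then hold placebo-phase events, and the per-100-patient-year rates for that group would divide events from one window by time from another.

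**Working it through.** No stated figure needs reproducing. The check is a comparison of sections plus some arithmetic on nominal days.

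**1. Requirement against plan.** The objectives name two presentations, open-label to Month 12 and overall. SAP 10.2, 10.2.2 and 10.2.3 deliver double-blind and overall. The omission does not look deliberate:
- SAP 3.9 lists changes to protocol-defined analyses (COVID-19 imputation, removal of the P1NP AUC) and not this one.
- SAP 3.2.1.2 still promises Month 12 safety analyses.
- SAP 10.2 moves injection-site and hypersensitivity events on the switch date into the open-label period, for which it then plans no TEAE table.

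**2. Can the open-label figure be recovered?** SAP 10.2 counts each participant once per display. For one sequence group with a common denominator, let D be double-blind incidence, O overall incidence and P post-switch incidence. Anyone counted in O had an event before the switch, after it, or both, so O ≤ D + P, and P ≤ O. Hence

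O − D ≤ P ≤ O.

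With assumed O = 80% and D = 60%, P lies between 80 − 60 = 20% and 80%. P also includes the 3-month follow-up, so it is not the open-label incidence either. Event counts, which the tables also show, can be subtracted, but the remainder is again open-label plus follow-up.

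**3. Event window against time at risk.** Inputs: 30-day months (protocol 8), first open-label dose at Month 6 (Day 180), last dose at Month 11 (Day 330), final visit at Month 15 (Day 450). For a placebo/romosozumab completer, events count over 450 days. SAP 10.2.1 does not define where romosozumab exposure ends, and its cross-reference for the definitions does not resolve, so three readings are shown.

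| Assumed end of exposure | Time at risk (days) | Event window ÷ time at risk |
|---|---|---|
| Month 11 dose | 330 − 180 + 1 = 151 | 450/151 = 2.98 |
| Month 11 dose + 30 days | 151 + 30 = 181 | 450/181 = 2.49 |
| Month 15 | 450 − 180 + 1 = 271 | 450/271 = 1.66 |

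The last row isolates the placebo phase, because follow-up is in both windows. In the first two rows, part of the excess is follow-up.

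**4. Single subjects.** For a subject with an event, SAP 10.2.2 uses time at risk up to the first occurrence. Take a placebo/romosozumab subject with a first event on Day 60 and first romosozumab on Day 180. The 10.2.1 formula gives 60 − 180 + 1 = −119 days. A subject who left while on placebo has no first romosozumab date, so no time at risk.

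**5. The two romosozumab-titled tables.** Under the SAP 10.2 inclusion rule, a placebo-phase event judged related to blinded IMP falls into the overall table of relationship to romosozumab, because no rule removes it. For the discontinuation table, the title can be read as leaving out events that stopped placebo, and no rule settles it.

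**The case against.** The best defence is that the authors meant the overall AE tables to cover romosozumab exposure only. SAP 7 computes overall-period compliance over the romosozumab treatment period, SAP 10.2.1 starts time at risk at the first romosozumab dose, and a negative time at risk cannot have been intended. SAP 3.1 also describes the placebo/romosozumab column as subjects who go on to receive romosozumab. This stands as evidence of intent, but it contradicts the event rule in 10.2. Even if accepted, it never isolates Months 6 to 12 in the romosozumab/romosozumab group.

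It is also fair to say that event counts can be subtracted and that deaths and study discontinuations occur once per subject, so their overall counts can be subtracted too. That does not help with repeatable TEAEs or with separating open-label from follow-up. The switch-date rule still has a use: it keeps those events out of the double-blind tables.

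A reader might infer three stronger things, which the documents do not support:
- **That open-label safety goes unreported.** Laboratory, vital-sign, ECG, antibody and disposition summaries all reach the open-label period.
- **That AEs which stopped placebo will be shown as leading to romosozumab discontinuation, even in subjects who never received it.** The title points the other way as readily, and the SAP has no rule on it.
- **That the gap between 15-month and 6-month incidence measures the distortion.** A longer, openly labeled window accrues more events in either sequence.

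**Conclusion.** The first part holds without qualification for TEAEs: a required presentation of a primary safety variable has no planned table, and its participant-level figure cannot be derived from those that are planned.

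The second part holds as an internal conflict. As written, the relationship-to-romosozumab table, and the numerators of the exposure-adjusted overall rates for placebo/romosozumab subjects, include placebo-phase events that the title or denominator excludes. The discontinuation table is ambiguous. The ratios of 1.66 to 2.98 rest on nominal visit days and an assumed end of exposure. They describe mismatched windows and do not predict a bias.

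The weight is moderate. SAP 10.2.3 plans no safety testing, no data are lost, and neither the randomized double-blind safety comparison nor any efficacy conclusion is affected.

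**What to change.** 1. In SAP 10.2 and 10.2.3, add open-label TEAE displays by sequence: overview, SOC/PT, serious, leading to discontinuation, and AEs of interest. Count onset after the End of DBPC Period date, plus the switch-date injection-site and hypersensitivity events that 10.2 already assigns to the open-label period, through the End of Open-Label Treatment Period date. Starting instead at the first open-label dose would count other switch-date events in both periods.
2. For the romosozumab-titled and per-100-patient-year overall tables, choose one of two routes. Either restrict them to events with onset on or after the first romosozumab dose, with the same switch-date rule, or retitle them and make time at risk match the event window in 10.2.
3. State whether AEs that stopped placebo belong in the romosozumab-discontinuation table, and define the end of romosozumab exposure in 10.2.1.

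The cost is SAP wording before database lock and repeat runs of existing table programs. The period dates are already defined in SAP 3.2.4, and no new data are needed.

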### 10.2.1 Time at risk of exposure

Time at risk for each subject represents the time a study participant is at risk for having an AE with romosozumab exposure period.

In this study, time at risk (years) during the overall study period is defined as:

(End of last romosozumab – Date of the first dose of romosozumab +1) / 365.25Study participant time at risk represents the time a participant is at risk for having an AE. The definitions for time at risk (in days) are outlined in Section Error! Reference source not found.. These definitions will be used for exposure-adjusted AE summaries.

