7 STUDY TREATMENT

7.1 Description of investigational medicinal product

For this study, romosozumab and placebo are considered IMP.

Subjects will be administered either romosozumab or placebo in a blinded manner for 6 months after which time, all subjects will receive active treatment (romosozumab) in an OL manner for 6 months.

Romosozumab will be supplied as a sterile, clear to opalescent, colorless to light yellow, preservative-free solution for sc injection in a single-use prefilled syringe (PFS). Each PFS contains 90mg/mL of romosozumab in 55mM acetate and 13mM calcium containing 6.0% w/v sucrose and 0.006% w/v polysorbate 20 at pH 5.2, with a deliverable volume of 1.17mL (105mg romosozumab solution for injection).

Placebo is supplied in a 1.17-mL PFS identical in appearance to romosozumab. Placebo will be stored and packaged the same as romosozumab.

Details of the IMP are provided in the IMP Handling Manual.

Subjects will be required to take daily calcium and vitamin D supplementation during the study; however, these protocol-required products are not considered IMP. Further information on the calcium and vitamin D supplementation is provided in Section 7.8.1.1.

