13.3.2 Final analysis

After all subjects have the opportunity to complete the Month 15 Visit, a further database snapshot or database lock will be executed. Based on these data, the remaining efficacy and safety analyses for Month 12 and the safety analyses for the overall study period, ie, the period from the start of double-blind treatment to the Month 15 Visit for each subject will be evaluated.

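### Overall-period adverse event rates count events from the first injection, placebo included, but divide by time on romosozumab only

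*SAP*

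**What the plan says.** **Numerator.** SAP 10.2 defines a TEAE as starting or worsening on or after the first dose of IMP and before the end-of-study (EOS) date. It produces displays for the double-blind period and "for the overall study period (treatment start through Month 15"). The inclusion rule for the latter is "For the overall period, TEAEs with a start date before or on the EOS date will be included"; it sets no lower bound at the first romosozumab dose. Protocol 7.1 states "For this study, romosozumab and placebo are considered IMP". Protocol 13.3.2 fixes the same span: "the safety analyses for the overall study period, ie, the period from the start of double-blind treatment to the Month 15 Visit".

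**Denominator.** SAP 10.2.1 gives time at risk in years during the overall study period as ("End of last romosozumab – Date of the first dose of romosozumab +1")/365.25. The end term is not defined, and the sentence that should lead to the definitions reads "The definitions for time at risk (in days) are outlined in Section Error! Reference source not found".

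**Rates.** SAP 10.2.2 divides subjects with an event (EAIR) or all events (EAER) by this time. For a subject with the event, the EAIR uses "time at risk in years to the first occurrence for the AE of interest".

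**Tables.** SAP 10.2.3 lists three overall-period tables per 100 patient-years: TEAE overview, TEAEs by SOC and PT, and serious TEAEs by SOC and PT. SAP 3.1 sets the final-analysis columns as placebo/romosozumab and romosozumab/romosozumab.

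**The concern.** A rate per person-year is interpretable only if events and time are counted over the same interval. Here the two intervals differ, and they differ by sequence. Romosozumab/romosozumab subjects start romosozumab on Day 1, so both clocks start together. Placebo/romosozumab subjects start it at Month 6, so their placebo months supply events but no time.

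The two columns stand side by side, so the placebo/romosozumab column would show the higher rate even if the true rates were identical. A reader could take that as a signal on switching to romosozumab, including in the serious TEAE table. Overall TEAE incidence is the primary safety variable of the open-label period (SAP 2.4.3.1).

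Two further cases fail under the formula as written. A first event during placebo has a negative time to occurrence. A placebo subject who never enters the open-label period can contribute events but has no time at risk.

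**Working it through.** **Inputs.** A month is 30 days (Protocol Table 5-1, footnote a). First IMP is on Day 1. The first open-label dose is at Month 6, target Day 180 (Table 5-1, footnote p; SAP 3.2.3). The last dose is at Month 11, 11 × 30 = Day 330, and EOS is at Month 15, 15 × 30 = Day 450 (Protocol 5.1.5). Full follow-up and one constant event rate in all periods and both sequences are assumed. The documents do not define the end term, so three readings are carried.

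**The plan's own figure.** SAP 2.5 gives romosozumab exposure as 12 and 6 months. With end = last dose + 30 days (Day 360), time at risk is 360 − 1 + 1 = 360 days and 360 − 180 + 1 = 181 days, which agrees to within a day.

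**EAER.** Events are counted over Days 1 to 450, that is 450 days in both columns. Inflation = 450 ÷ time at risk.

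| End taken as | Rom/rom time (days) | Pbo/rom time (days) | Rom/rom inflation | Pbo/rom inflation | Ratio |
|---|---|---|---|---|---|
| Last dose | 330 | 151 | 450/330 = 1.36 | 450/151 = 2.98 | 2.19 |
| Last dose + 30 days | 360 | 181 | 450/360 = 1.25 | 450/181 = 2.49 | 1.99 |
| EOS | 450 | 271 | 1.00 | 450/271 = 1.66 | 1.66 |

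A true 10 events per 100 patient-years would be printed, placebo/romosozumab against romosozumab/romosozumab, as 29.8 v 13.6, 24.9 v 12.5 or 16.6 v 10.0. The ratio does not depend on the true rate. With EOS 14 days early, as Protocol 8 allows, the last ratio is 257 v 436 days, or 1.70.

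**EAIR.** With first-event hazard h per day, the expected numerator per subject is 1 − exp(−450h). The expected denominator is the integral of (t − c)·h·exp(−ht) over 0 to 450 days, plus total time at risk × exp(−450h), where c = 179 days for placebo/romosozumab and 0 otherwise. At a true 10 per 100 patient-years this gives 30.6 v 13.3, 25.7 v 12.3 or 17.3 v 10.0 for the three readings.

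For common events the formula breaks down. An onset on Day 50 contributes 50 − 180 + 1 = −129 days. If such times are summed as written, a true 100 per 100 patient-years becomes 579 v 116, 484 v 111 or 325 v 100. At 200 per 100 patient-years the placebo/romosozumab denominator is negative under all three readings.

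**Matching the numerator only.** If placebo-phase events were dropped but the end term left open, placebo/romosozumab inflation is 271/151 = 1.79, 271/181 = 1.50 or 1.00. The ratios to the other column are then 1.32, 1.20 or 1.00, so the end date matters as well as the start.

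**Confidence limits.** SAP 10.2.2 prints the EAIR limits as chi-square quantiles divided by 2, which are limits for a count. For an assumed n = 20 and 180 patient-years, the EAIR is 20/180 × 100 = 11.1. The printed formulas give 12.2 and 30.9, which exclude the estimate. Dividing by 180 and multiplying by 100 gives 6.8 and 17.2.

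**The case against.** The strongest reply is that a romosozumab-only analysis was intended. SAP 10.2.1 speaks of risk during romosozumab exposure. SAP 7 computes overall-period compliance over the romosozumab treatment period. Several overall-period tables in SAP 10.2.3 refer to romosozumab where their double-blind counterparts refer to IMP. On that reading only events on romosozumab count, and the ratio falls to between 1.0 and 1.3. The intent is plausible, but no sentence limits the numerator, and SAP 10.2 sets the opposite window explicitly.

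Other points carry some weight:

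- The extreme EAIR values need a program that sums negative time. With time floored at zero and capped at each subject's total, a true 100 per 100 patient-years gives 342, 296 or 221 in the placebo/romosozumab column instead of 579, 484 or 325. The uncommon-event values barely move (30.1 v 13.4, 25.2 v 12.3, 17.0 v 10.0). The EAER result does not depend on this.
- Ending at the last dose date is the least natural reading, since SAP 10.1 adds 30 days in its adjusted exposure formula. Without it the ratio is 1.7 to 2.0.
- SAP 10.2.2 also says these tables are by actual treatment, and SAP 3.5.3 puts anyone given romosozumab in the romosozumab group. Pooling the planned 200 and 100 subjects would remove the contrast but not the error: 300 × 450 ÷ (200 × 330 + 100 × 151) = 1.66, and likewise 1.50 or 1.15 for the other two end dates.
- The missing division in the confidence limits is probably a notational omission.
- The tables are descriptive, and SAP 10.2.3 plans no safety testing.

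**Conclusion.** The concern holds, with high confidence on the text: as written, numerator and denominator of the overall-period EAIR and EAER cover different spans, and the plan would produce wrong rates. On the planned schedule, with full follow-up and equal constant rates, the placebo/romosozumab EAER is overstated 1.7- to 2.2-fold relative to romosozumab/romosozumab. The width of that range comes from the undefined end date. Under the two shorter readings the romosozumab/romosozumab rate is itself overstated, 1.36- or 1.25-fold, because follow-up events are counted without follow-up time.

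This should be fixed, but its reach is limited to the three tables per 100 patient-years. Crude n (%) [events], the randomised double-blind comparison and all efficacy analyses are untouched.

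**What to change.** Use one start and one end for both events and person-time in each column. Either of two definitions works, and each returns the distortion factor to 1.00:

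- **By sequence:** first IMP to EOS for events and time.
- **By romosozumab exposure:** first romosozumab dose to one stated cut-off, counting only events in that window. Switch-day events follow the existing rule, "If a TEAE occurs on the date of switch from the DBPC period to the OL period, the event is attributed to the DBPC treatment", with its exception for injection-site reactions and hypersensitivity.

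The SAP should also:

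- define the end term in 10.2.1 and repair the cross-reference;
- stop time at first onset for the EAIR only, and use total time in the window for the EAER;
- say how placebo subjects who never receive romosozumab are handled;
- state that both Poisson limits are divided by total person-years and multiplied by 100.

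The cost is SAP wording and table programming; no new data are needed.
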